PROTOCOL

Precision medicine in liver transplantation: a personalised approach to immunosuppression

Protocol Number: LT001 Version: 2 Date: 2/5/19

Author/s:

[name] [name] A/[name] [name] A/[name] [name]

> **Sponsor/s:** Austin Health

CONFIDENTIAL

This document is confidential and the property of The University of Melbourne and Austin Health. No part of it may be transmitted, reproduced, published, or used without prior written authorization from the institution.

Statement of Compliance

This document is a protocol for a research project. This study will be conducted in compliance with all stipulation of this protocol, the conditions of the ethics committee approval, the NHMRC National Statement on ethical Conduct in Human Research (2007) and the Note for Guidance on Good Clinical Practice (CPMP/ICH-135/95).

TABLE OF CONTENTS

CONTENTS

Та	Fable of Contents 3			
	1.	Glossary of Abbreviations & Terms	. 6	
	2.	Study Sites	. 6	
	а	. Study Location	. 6	
	3.	Introduction/Background Information	. 6	
	а	. Lay Summary	. 6	
	b	. Introduction	. 7	
	C.	Background information	. 8	
	4.	Study Objectives	. 8	
	a	. Hypothesis	. 8	
	b	. Study Aims	. 9	
	C.	Outcome Measures	. 9	
5.	S	tudy Design	10	
	a	. Study Type & Design & Schedule	10	
(6.	Study Population	12	
	a	Recruitment Procedure	12	
	b	. Inclusion Criteria	13	
	C.	Exclusion Criteria	13	
	d	Consent	13	
7.	Ρ	articipant Safety and Withdrawal	13	
	a	Risk Management and Safety	13	
	b	. Handling of Withdrawals	13	
	C.	Replacements	14	
8.	S	tatistical Methods	14	
	a	. Sample Size Estimation & Justification	14	

	b.	Power Calculations	14		
	C.	Statistical Methods To Be Undertaken	14		
9.	Sto	rage of Blood and Tissue Samples	15		
a Sa	a. Details of where samples will be stored, and the type of consent for future use of samples				
10.	0. Data Security & Handling				
	a.	Details of where records will be kept & How long will they be stored	15		
	b.	Confidentiality and Security	15		
11.	Re	ferences	15		

STUDY SYNOPSIS

Title:	Precision medicine in liver transplantation: a personalised approach to immunosuppression		
Short Title:	Personalising immunosuppression in liver transplantation		
Design:	Single-centre prospective observational cohort study		
Study Centres:	Austin Health		
Hospital:	Austin Hospital		
Study Question:	What is the utility of the combination of the novel QuantiFERON-Monitor (QFM) and donor-specific cell free DNA (dscfDNA) blood tests in monitoring and managing immunosuppression post liver transplantation (LT)?		
Study Objectives:	To determine the utility of the combined QFM and DNA (QFM- dscfDNA) tests in monitoring and managing immunosuppression post LT.		
Primary Objectives:	To examine if the QFM-DNA tests can be used to accurately diagnose acute rejection and infective complications after LT.		
Secondary Objectives	To examine if the QFM-DNA tests can be used to predict acute rejection or infective complications, monitor treatment responses, and improve healthcare resource utilisation.		
Inclusion Criteria:	 Age 18 years and above Undergoing LT at Austin Health Can provide written informed consent 		
Exclusion Criteria:	 Aged under 18 years Undergoing multi-organ transplantation Unable to provide written informed consent at any stage 		
Number of Planned Subjects:	210		
Investigational product:	Nil		
Safety considerations:	Participants will be required to have serial additional blood sampling, performed when blood tests for the standard of care for LT occur wherever possible. They may be subjected to mild physical or psychological distress during venepuncture. There will be no deviation from standard of care treatment.		
Statistical Methods:	Receiver-operator characteristics analysis.Logistic regression analysis.		
Subgroups:	Nil		

1. GLOSSARY OF ABBREVIATIONS & TERMS

Abbreviation	Description (using lay language)
QFM	QuantiFERON-Monitor
dscfDNA	Donor specific cell free DNA
QFM-cfdsDNA	Combined QuantiFERON-Monitor and donor specific cell free DNA
LT	Liver transplantation
LFTs	Liver function tests
tBPAR	Treatment responsive biopsy proven acute rejection
FBE	Full blood count
UEC	Urea and electrolytes
AUC	Area under the receiver operator curve
PCR	Poylmerase chain reaction
MBS	Medicare Benefits Schedule
PBS	Pharmaceutical Benefit Scheme
ONJCRI	Olivia Newtown John Cancer Research Institute
LTU	Liver Transplant Unit

3. INTRODUCTION/BACKGROUND INFORMATION

a. LAY SUMMARY

Liver transplantation is the only effective treatment for many patients with liver disease. Due to advances in medical care, liver transplantation now has acceptable mortality and morbidity. Both locally and globally, the number of liver transplants performed each year continues to increase.

Long-term, the success of a liver transplant depends on a fine balance: suppressing the immune system to avoid organ rejection, whilst maintaining it to prevent infection. Despite careful monitoring with standard blood tests, most patients will experience episodes of rejection and/or infections. Diagnosing these complications often requires expensive medical

imaging and an invasive liver biopsy, prior to treatment with immunosuppression adjustment. There is a clear need for innovative tools to 'personalise' immunosuppression, and improve patient outcomes, whilst reducing healthcare resource utilisation.

Researchers at Austin Health have pioneered the study of two novel blood tests -QuantiFERON-Monitor to assess immune function, and donor-specific cell free DNA to measure organ injury. This prospective observational cohort study aims to advance current knowledge, by determining the utility of combining these two tests in monitoring and managing immunosuppression post liver transplantation.

We aim to recruit 210 adult liver transplant recipients who will be followed up for 12 months. Participants will be required to have serial additional blood sampling, performed when blood tests for the standard of care for LT occur wherever possible.

b. INTRODUCTION

The long-term success of LT is finely balanced between adequately suppressing the recipient immune system to minimise organ rejection, while simultaneously maintaining it at a level that prevents infective complications. Immunosuppression is dosed empirically and adjusted according to the temporal changes to LFTs, drug levels or the onset of rejection or infective complications. Despite the judicious use of immunosuppression, nearly half the recipients develop an episode of rejection and up to 70% experience infective complications¹⁻⁴. These complications impact on patient quality of life⁵ and are costly to manage (up to USD \$83,000 per episode)⁶.

LFTs are extremely sensitive tests for organ injury but have poor specificity for LT complications⁷. As a screening tool, they can lead to a series of radiological and endoscopic investigations that often culminate in an invasive liver biopsy to confirm the clinical event⁸. Acute rejection is treated with increased doses of immunosuppressants while infection necessitates dosage reduction. This relatively 'reactive' approach precludes preventive intervention by predictive adjustments.

Researchers at Austin Health have shown that the use of an immune monitoring blood test, QuantiFERON-Monitor (QFM), identifies recipients at risk of early rejection or infective complications. Austin Health researchers have also developed a novel blood test to rapidly measure organ injury using donor-specific cell-free DNA (dscfDNA).

We propose a prospective observational cohort study of 210 patients who are LT recipients followed up for 12-months to determine the utility of combining the two blood tests (QFM-dscfDNA) in monitoring and managing immunosuppression post LT. Our primary hypothesis is that the QFM-dscfDNA tests can be used to accurately diagnose the occurrence of rejection or infective complications after liver transplantation. The secondary hypotheses are that QFM-dscfDNA tests can be used to predict acute rejection or infective complications, monitor treatment responses and improve healthcare resource utilisation.

There is a clear and urgent need for accurate clinical tools to personalise immunosuppression. Confirmation of our hypotheses facilitates a "predictive" rather than the current "reactive" approach to immunosuppression. Our approach can potentially minimise the need for complex diagnostic tests including ultrasound, computed tomography, magnetic resonance imaging, endoscopy and liver biopsies - with significant clinical and economic benefits.

If positive, the findings of this study will lead to a prospective randomised multi-centre trial comparing the standard and precision approaches in LT. If validated in LT, we foresee that the predictive approach to immunosuppression is readily translatable for evaluation in other solid organ transplantations. With over 125,000 solid organ transplantations being performed

worldwide annually, the clinical and economic implications of this study could be substantial.

c. BACKGROUND INFORMATION

i. SCIENTIFIC BACKGROUND

The long-term success of LT is finely balanced between adequately suppressing the recipient immune system to minimise organ rejection, while simultaneously maintaining it at a level that prevents infective complications. Immunosuppression is dosed empirically and adjusted according to the temporal changes to LFTs, drug levels or the onset of rejection or infective complications. Despite the judicious use of immunosuppression, nearly half the recipients develop an episode of rejection and up to 70% experience infective complications¹⁻⁴. These complications impact on patient quality of life⁵ and are costly to manage (up to USD \$83,000 per episode)⁶.

LFTs are extremely sensitive tests for organ injury but have poor specificity for LT complications⁷. As a screening tool, they can lead to a series of radiological and endoscopic investigations that often culminate in an invasive liver biopsy to confirm the clinical event⁸. Acute rejection is treated with increased doses of immunosuppressants while infection necessitates dosage reduction. This relatively 'reactive' approach precludes preventive intervention by predictive adjustments.

ii. PRELIMINARY RESEARCH

Researchers at Austin Health have pioneered the study of two rapid and low-cost blood tests in LT: one that measures the immune function of the recipient, and one that quantifies organ injury.

The first of these is QFM. Based on the widely available QuantiFERON-Gold test, QFM involves stimulating whole blood collected from the patient with innate and adaptive immune ligands, and quantifying interferon gamma release. Sood et al. have evaluated QFM, and gained experience in its application in LT⁹⁻¹¹. They found that QFM accurately identifies recipients at risk of developing biopsy-proven acute rejection requiring treatment (tBPAR) or infective complications within one month after LT.

The second test is a novel DNA-based laboratory assay based on the following concepts. Firstly, that during normal cellular turnover, the donor organ continuously sheds dscfDNA into the recipient circulation. Secondly, that when the donor organ is injured, dscfDNA increases. This can be quantified using next-generation sequencing techniques, however these are complex, labour-intensive and expensive¹²⁻¹⁴. Goh et al. therefore developed a polymerase chain reaction technique to quantify dscfDNA that is accurate, rapid and economic^{15,16}. They subsequently performed a pilot study in patients post LT comparing dscfDNA to clinical events, and found that dscfDNA levels were low in well patients, but elevated in those with tBPAR¹⁷.

4. STUDY OBJECTIVES

a. HYPOTHESIS

The primary hypothesis is that the QFM-dscfDNA tests can be used to accurately diagnose the occurrence of acute rejection and infective complications after LT.

The secondary hypotheses are that the QFM-dscfDNA tests can be used to:

- Predict acute rejection and infective complications.
- Monitor treatment responses.
- Improve healthcare resource utilisation.

b. STUDY AIMS

- To examine if the QFM-dscfDNA tests can be used to accurately diagnose acute rejection and infective complications after LT.
- To examine if the QFM-dscfDNA tests can be used to predict acute rejection or infective complications, monitor treatment responses, and improve healthcare resource utilisation.

c. OUTCOME MEASURES

i. DEFINITION OF CLINICAL EVENTS:

- Rejection: The gold standard for diagnosing acute rejection is based on histopathologic grading on liver biopsy. It is often difficult to differentiate mild rejection from ischemia-related cholestasis early after LT and clinical evaluation may lead to observation rather than active treatment if temporal improvement is demonstrated. We thus employed the strict definition requiring consistent histology and treatment of rejection (tBPAR), an acceptable standard for clinical trials^{18,19}.
- Infective complications: Infection endpoints will be defined according to the criteria of 'no', 'probable' or 'definite' infection derived from the international sepsis forum consensus conference on '*Definitions of Infection in the Intensive Care Unit*^{'20}.

i. VARIABLES TO BE MEASURED:

- Standard of care clinical variables: Donor and recipient factors such as donor risk index, model for end-stage liver disease score, waiting list time, primary indication for transplantation, operative factors and immunosuppression regimens can influence post LT outcomes. These characteristics will be prospectively recorded for analysis.
- Standard of care blood tests: Routine blood tests including full blood count (FBE), urea and electrolytes (UEC), LFTs and serum drug levels are used for clinical decision making as a standard of care. The results of each test will be prospectively recorded.
- QFM: Recipient blood samples will be processed within eight hours of venesection. The blood samples will be stimulated with the QFM immune ligands anti-CD3 and R848¹⁴, incubated overnight at 37 °C and fractionated. The plasma component will then be stored at -80 °C. A batched analysis of the stored plasma will be performed at the end of the 12-month follow-up using ELISA to quantify IFNγ as IU/m, so results will not influence the decision-making of the treating clinicians.
- dscfDNA: Recipient blood samples will be processed within three hours of venesection. The blood samples will be fractionated into the leukocyte-rich 'buffycoat' and plasma components. Donor blood samples will be obtained during organ procurement, in accordance with the Human Research Ethics Committee for Donate Life and the Australian Red Cross Blood Services (application in progress). All samples will be stored at -80 C. Genomic DNA will first be extracted from the buffy coats of the organ donors and the pre-transplant recipient. High resolution melting analyses will be used to genotype each donor-recipient pair using a panel of small biallelic deletion/insertion polymorphisms¹⁶. This step will be performed once for each donor-recipient pair to determine a set of allelic sequences that are present in the donor and absent in the recipient for the detection of dscfDNA. Subsequently, we will utilise our rapid and readily performed methodology to quantify dscfDNA¹⁷. Our novel assay design enables the amplification of dscfDNA using allelic breakpoints that are only present in donor-specific alleles. Combined with the Bio-Rad droplet digital polymerase chain reaction (PCR) platform, dscfDNA can be measured with unprecedented accuracy in the recipient's blood, in copies/mL of recipient plasma. As with QFM, the samples of each recipient will be batched for analysis at the end of the 12-month follow-up, so results will not influence the decision-making of the treating clinicians.
- Health expenditure: The costs associated with inpatient and outpatient healthcare resource usage, investigations medications and the QFM-dscfDNA tests will be

retrieved from the Austin Health Department of Finance, Austin Health as well as the Medicare Benefits Schedule (MBS) and Pharmaceutical Benefit Scheme (PBS).

ii. PRIMARY ENDPOINTS:

The accuracy of QFM and dscfDNA, alone and in combination, compared to LFTs to diagnose:

- The first episode of tBPAR, as measured by the area under the receiver operator curve (AUC).
- The first episode of infective complication, as measured by the AUC.

iii. SECONDARY ENDPOINTS:

- The accuracy of QFM and dscfDNA, alone and in combination, in predicting the occurrence of imminent tBPAR and infective complications before clinical manifestation of the event.
- The performance of QFM and dscfDNA, alone and in combination, in monitoring treatment responses of tBPAR and infective complications, as compared to routine blood tests.
- Healthcare expenditures and cost-effectiveness of QFM-dscfDNA, as measured using hospital, PBS and MBS data.

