8. STATISTICAL METHODS

a. SAMPLE SIZE ESTIMATION & JUSTIFICATION

We propose enrolling a total of 210 LT recipients during a three-year recruitment period. This timeframe is anticipated to be easily feasible as the LTU performs an average of 75 adult LTs each year. Most recipients will fulfil the trial's inclusion and exclusion criteria; hence non-eligibility (including refusal of informed consent) is anticipated to be low (about 5%). In addition, lost-to-follow-up (including death) is anticipated to be very low (about 1-2%) during the 12-month follow-up².

In preliminary research from Austin Health¹⁶, 31% of the recipients experienced tBPAR as the first event after LT while 41% experienced a 'probable'/'definite' infective complication as the first event after LT, both within a 12-month follow-up period. To be conservative, we assume 30% of our recruited recipients will experience at least one tBPAR and 40% at least one infective complication. The sample size of 210 LT recipients will allow us to estimate a fair AUC of 0.7 using a two-sided 95% confidence interval with precision \pm 0.081 for tBPAR and \pm 0.075 for infection and a good AUC of 0.8 with a precision of \pm 0.075 for tBPAR and \pm 0.069 for infection^{21,22}.

b. POWER CALCULATIONS

This sample size will provide a power of 99.7% to show that the combination has any ability to discriminate between those with and without tBPAR and 99.9% power between those with and without infection, (null hypothesis AUC of 0.5), assuming that we observe a fair AUC of 0.7 with 5% alpha²¹.

c. STATISTICAL METHODS TO BE UNDERTAKEN

All participants will be included in the final analyses. Diagnostic performance of QFM and dscfDNA combined for the first tBPAR and the first 'probable'/'definite' infective complication will be assessed by evaluation of sensitivity, specificity, the positive and negative predictive value and diagnostic accuracy. Diagnostic accuracy will be evaluated by determining the AUC and two-sided 95% confidence interval. Given that QFM and dscfDNA outcomes are measured repeatedly over 12 months, we will initially summarise these outcomes across time-points using the average, nadir, standard deviation and slope and fit a logistic regression model.

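### The secondary prediction endpoint names no comparator, so the study could report that QFM-dscfDNA predicts rejection or infection when routine LFTs predict equally well

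*Protocol*

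**What the plan says.** Section 4.c lists three accuracy or performance endpoints.

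- **Diagnosis (primary).** The accuracy of QFM and dscfDNA, "alone and in combination, compared to LFTs to diagnose" the first tBPAR and the first infective complication.
- **Prediction (secondary).** The accuracy of the same tests "in predicting the occurrence of imminent tBPAR and infective complications before clinical manifestation of the event". No comparator follows.
- **Treatment response (secondary).** Their performance "in monitoring treatment responses of tBPAR and infective complications, as compared to routine blood tests".

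Section 8.b powers the study to show that the combination "has any ability to discriminate between those with and without tBPAR", and likewise for infection, against a null AUC of 0.5. Section 8.c plans to compare the AUC of each single test with that of the combination and to derive a threshold for QFM and dscfDNA. LFTs appear in section 8.c only in a joint longitudinal model that is to be explored.

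Prediction is one of the secondary hypotheses in section 4.a. On the hypotheses as a whole, the Introduction (section 3.b) says "Confirmation of our hypotheses facilitates a" predictive approach in place of the present reactive one. It adds: "If positive, the findings of this study will lead to a prospective randomised multi-centre trial comparing the standard and precision approaches in LT".

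**The concern.** The Introduction's claim is relative: predictive monitoring is set against current care. By the protocol's own account, current care already adjusts immunosuppression on changes in LFTs and on drug levels, and LFTs are very sensitive to organ injury. LFTs taken before an event may therefore carry some predictive signal themselves. An AUC for the new tests, reported alone, shows that they discriminate. It does not show that they discriminate better than results the clinician already has.

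This comparator is part of the endpoint's definition, which section 4.c fixes, and section 4.c supplies one for the endpoints on either side. An SAP that followed the section faithfully would not need any LFT contrast for prediction. The study could then report successful prediction, and cite it as grounds for the follow-on trial, with no evidence of a gain over routine bloods.

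**Working it through.** **Inputs from the protocol (sections 8.a and 8.b).** N = 210. tBPAR in 30%: 0.30 × 210 = 63 with and 147 without. Infection in 40%: 0.40 × 210 = 84 with and 126 without. Null AUC 0.5, alpha 5% (taken as two-sided).

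**Assumptions.** The protocol gives no AUC for LFTs, so a range is shown. Each participant is taken to have one usable pre-event score. Prediction is taken to be judged by a test of AUC against 0.5, because that is the only null value in the document.

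**Formula.** Binormal variance (Obuchowski): V = 0.0099 × exp(−a²/2) × [(5a² + 8) + (a² + 8)/k], with a = 1.414 × z(AUC), k = non-events/events and SE = √(V/events).

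**Step 1: reproduce the plan's figures.**

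- At AUC 0.7, a = 0.7415. For tBPAR, k = 147/63 = 2.333, V = 0.1084, SE = √(0.1084/63) = 0.0415, and 1.96 × SE = 0.081. For infection, k = 126/84 = 1.5, V = 0.1237, SE = √(0.1237/84) = 0.0384, and the half-width is 0.075.
- At AUC 0.8 the half-widths are 0.075 and 0.069. All four match section 8.a.
- Power = Φ((0.2 − 1.96 × SE₀)/SE₁), where SE₀ is the SE at AUC 0.5 (0.0424 for tBPAR, 0.0396 for infection). For tBPAR, (0.2 − 0.0831)/0.0415 = 2.82, giving 99.76%. For infection, (0.2 − 0.0777)/0.0384 = 3.19, giving 99.93%. Section 8.b states 99.7% and 99.9%. The Hanley-McNeil variance gives 99.72% and 99.93%.

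**Step 2: how often does a test with no gain over LFTs still beat 0.5?** Let the combination and LFTs share the same pre-event AUC, so that the true difference is zero. The same formula, with (AUC − 0.5) in place of 0.2, gives:

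| Shared AUC | tBPAR | Infection |
|---|---|---|
| 0.60 | 66% | 71% |
| 0.65 | 94% | 97% |
| 0.70 | 99.8% | 99.9% |

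For example, tBPAR at 0.60: (0.10 − 0.0831)/0.0423 = 0.40, and Φ(0.40) ≈ 0.66.

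**Step 3: what N = 210 can show once LFTs are the comparator.** Assume AUC 0.8 for the combination and 0.7 for LFTs, with correlation r between the two estimates. SE of the difference = √(SE₁² + SE₂² − 2r·SE₁·SE₂), and power = Φ(0.1/SE − 1.96). For tBPAR at r = 0.5: √(0.0385² + 0.0415² − 0.0385 × 0.0415) = 0.0401, and Φ(0.1/0.0401 − 1.96) ≈ 70%.

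| r | tBPAR | Infection |
|---|---|---|
| 0 | 42% | 48% |
| 0.3 | 56% | 63% |
| 0.5 | 70% | 77% |
| 0.7 | 90% | 94% |

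**The case against.** The best reply has four parts.

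- **No pass mark is set for prediction.** The null of 0.5 belongs to the power calculation for telling participants with an event from those without. The prediction endpoint is worded as accuracy, with no test. This is correct, so Step 2 is an illustration and not the plan's own decision rule. It does not supply the missing comparator.
- **The consequence is mild.** The predictive statement is motivating text, and the only action named is a randomised trial of standard against precision care, which would itself make the comparison. This stands. A reader might infer that practice would change directly on this endpoint, but the documents do not support that: both assays are batched until the end of follow-up, and treatment stays at standard of care.
- **LFTs are not absent from the longitudinal work.** They enter the joint model in section 8.c. That model is exploratory and is not a head-to-head comparison of predictive accuracy.
- **An SAP is announced.** It may add the contrast, but section 4.c as written does not call for it.

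A reader might also infer that any single favourable result among many unranked secondary comparisons would count as confirmation. The protocol does not say so. It states no one-win rule, its hypotheses concern the combined test, and the ordering and error control of secondary endpoints may properly be left to the SAP.

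**Conclusion.** The point holds as a gap in the endpoint's definition. As fixed in section 4.c and analysed in section 8.c, the prediction endpoint cannot show that the new tests predict better than current monitoring, which is the contrast the Introduction draws. A combination with no advantage over LFTs would probably still look successful against 0.5, with probability from about two-thirds at a shared AUC of 0.60 to near certainty at 0.70.

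Those figures rest on an assumed LFT AUC, the protocol's event rates, a test against 0.5, and a usable pre-event score for every participant. The protocol does not say how many events will have an earlier usable sample; fewer would lower the percentages. The gap itself depends on none of these assumptions. It is worth correcting because a secondary endpoint carries much of the study's rationale, but it does not affect the primary endpoints, which already name LFTs.

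**What to change.** In section 4.c, complete the prediction endpoint by adding a comparison with LFTs and other routine blood tests taken at the same pre-event time point. For tBPAR and for infection, report the paired difference in AUC (combination versus LFTs or routine tests) with its 95% CI. In section 3.b, rest the predictive-versus-reactive statement on that difference.

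The cost is a wording change and one paired AUC analysis per event. Routine results are already to be recorded prospectively, and study samples are to be drawn alongside routine ones wherever possible, so no new patients or samples are required.

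The downside is that the claim becomes harder to make. At the assumed 0.8 versus 0.7, power runs from about 42% to 90% for tBPAR and from 48% to 94% for infection as the correlation goes from 0 to 0.7. The difference should therefore be presented as an estimate with its interval rather than as a pass or fail.

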5. STUDY DESIGN

a. STUDY TYPE & DESIGN & SCHEDULE

ii. STUDY DESIGN:

This is a prospective observational single-centre cohort study of 210 patients who are LT recipients followed up for 12-months, to determine the utility of the QFM-dscfDNA in monitoring and managing immunosuppression post LT.

Consenting adults (aged 18 years and over) undergoing LT at Austin Health will be invited for enrolment in the study in the pre-transplant clinic, during outpatient assessment or on admission to hospital prior to LT. Written informed consent will be obtained prior to enrolment. Recipients under 18 years of age, those who do not consent their participation and those who are undergoing multi-organ transplantation will be excluded from the study.

The design of this study will enable the researchers to examine if the QFM-dscfDNA tests can be used in LT recipients to accurately diagnose and predict acute rejection and infective complications, monitor treatment responses, and improve healthcare resource utilisation.

iii. INTERVENTION:

Participants will receive the standard of care after LT, with serial additional blood sampling required for QFM-dscfDNA testing:

Standard of care after LT: Clinical care of LT recipients is directed by a team of experienced clinicians. Potential recipients are selected based on clinical urgency and donor–recipient matching. LT is performed as per protocol. Routine immunosuppression comprising steroids, a calcineurin inhibitor and an antimetabolite will be prescribed. Routine protocol liver biopsies are not performed to monitor organ health. Routine blood tests (FBE, UEC, LFTs and serum drug levels) are performed regularly to monitor the clinical course. Recipients are closely followed up as outpatients after discharge. Complications after LT may result in the deterioration of clinical status and abnormalities on routine blood tests. Imaging,

endoscopy and/or liver biopsies are performed for diagnosis and managed accordingly.

• Additional blood sampling: The intervention requires serial additional blood sampling of recipients, which will be performed when routine blood sampling for standard of care is undertaken wherever possible, to reduce the need for additional venesection.

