7. PARTICIPANT SAFETY AND WITHDRAWAL

a. RISK MANAGEMENT AND SAFETY

In this prospective observational cohort study, there will be no deviation from standard of care treatment.

Participants will be required to have serial additional blood sampling, performed when blood tests for the standard of care for LT occur wherever possible. This is the reduce the need for additional venepuncture, and is anticipated to be highly feasible due to the frequency of blood tests required for the standard of care post LT.

Participants may be subjected to mild physical (pain, bruising, dizziness) or psychological distress (anxiety) during venepuncture. They will be informed this low risk prior to enrolment, and provided with access to medical or counselling services if required.

b. HANDLING OF WITHDRAWALS

Participants who withdraw from this study will have the opportunity to have a withdrawal interview with the research coordinators, in order to voice their concerns and to receive

answers for any questions. Unless specified by the participant, already collected data will be kept for analysis and future research purposes. However, in cases where initial consent has been obtained from their person responsible and the patient then wishes to withdraw this consent, all of their data collected for research purposes will be securely destroyed.

c. Replacements

Withdrawn participants will be replaced in this study

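### The cohort can observe costs under standard care and the cost of the tests, but not an improvement in resource use or the cost-effectiveness of test-guided care

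*Protocol*

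**What the plan says.** **The claim.** Protocol section 4.a lists "Improve healthcare resource utilisation" among three secondary hypotheses, under a stem about what the tests can be used for. Section 4.b and the synopsis repeat it as an aim and an objective. Section 5.a.ii says "The design of this study will enable the researchers to examine if the QFM-dscfDNA tests can be used in LT recipients" for a list of purposes that includes better resource use. Section 4.c.iii sets the endpoint: "Healthcare expenditures and cost-effectiveness of QFM-dscfDNA, as measured using hospital, PBS and MBS data".

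**The design.** For QFM, section 4.c states "A batched analysis of the stored plasma will be performed at the end of the 12-month follow-up using ELISA", with the reason "so results will not influence the decision-making of the treating clinicians". It gives the same timing and reason for dscfDNA. Section 5.a.ii describes one group: "This is a prospective observational single-centre cohort study of 210 patients". Section 7.a adds: "In this prospective observational cohort study, there will be no deviation from standard of care treatment".

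**The costs to be collected.** Under health expenditure, section 4.c covers inpatient and outpatient resource use, investigations, medications and the two tests themselves.

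**The later comparison.** The introduction (section 3.b) says: "If positive, the findings of this study will lead to a prospective randomised multi-centre trial comparing the standard and precision approaches in LT".

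**The concern.** Cost-effectiveness is a contrast: the costs and outcomes of one way of managing patients set against those of another. Here the relevant contrast is test-guided care against standard care, and only the second takes place. Yet the endpoint speaks of cost-effectiveness as something to be measured from administrative data, and the design section says without qualification that improved resource use can be examined.

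At stake is what may be concluded on one of three secondary hypotheses. Read literally, the endpoint adds the cost of the tests to the cost of standard care, with no saving or health effect that could be attributed to the tests. Any statement of improvement would have to come from outside the observed data. The introduction ties confirmation of the hypotheses to a change in how immunosuppression is approached and to a further trial, so the economic statement should claim no more than the design supports.

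**Working it through.** **1. The plan's own figures.** No figure is given for resource use or cost-effectiveness; the sample-size section concerns AUC only. Those figures were checked to confirm that the point does not touch them.

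- Inputs from section 8: 210 recipients; 30% with tBPAR (0.30 × 210 = 63, leaving 147 without); 40% with infection (0.40 × 210 = 84, leaving 126).
- Binormal AUC variance: V = 0.0099 · exp(−a²/2) · [(5a² + 8) + (a² + 8)/k], with a = 1.414 · z(AUC) and k = non-events/events. The half-width is 1.96 · √(V/events).

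| Event | AUC | Stated | Recomputed |
|---|---|---|---|
| tBPAR | 0.7 | 0.081 | 0.0813 |
| Infection | 0.7 | 0.075 | 0.0752 |
| tBPAR | 0.8 | 0.075 | 0.0754 |
| Infection | 0.8 | 0.069 | 0.0690 |

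Two-sided power at 5% for AUC 0.7 against 0.5 comes to 99.76% (tBPAR) and 99.93% (infection) with this variance, and to 99.72% and 99.93% with the Hanley-McNeil variance. The plan states 99.7% and 99.9%. The diagnostic aim is sound as calculated.

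**2. What a measured contrast needs.** Let C be mean cost and E mean outcome, with T for test-guided and S for standard care:

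- Incremental cost = C_T − C_S
- Incremental effect = E_T − E_S
- Cost-effectiveness ratio = (C_T − C_S)/(E_T − E_S)

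| Quantity | Observed in this study? | Participants |
|---|---|---|
| C_S, E_S | Yes, from standard care | 210 |
| Cost of the tests | Yes, listed under health expenditure | 210 |
| C_T, E_T | No, results are withheld until after follow-up | 0 |

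With no observations for C_T and E_T, neither difference can be calculated from the data. Section 8.c points the same way: the test thresholds are to be established by this study, so no test-guided pathway exists during follow-up that could be costed.

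**3. What can be projected.** A modelled incremental cost per recipient has the form

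ΔC = (tests per recipient × cost per test) + Σ (change in use of each resource × its unit cost).

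Unit costs and the cost per test can come from the study's cost data. The change in use of each resource depends on test accuracy, which the study estimates, and on how clinicians would respond to a result, which it does not observe. That response must be assumed, so the result is a projection.

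**4. The number of tests.** Section 5 gives 11 × 210 = 2310 scheduled tests and 3 × 150 = 450 event-driven tests, 2310 + 450 = 2760 in all. The total is arithmetically right. It reflects a research sampling schedule, and its second part rests on an estimate of about 150 events. It is neither an upper limit nor the test volume of a clinical pathway.

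**The case against.** The strongest reply is that the protocol claims less than it may seem to. The hypotheses are about what the tests can be used for, the introduction speaks of potential reductions in investigations, and the comparison of standard with precision care is explicitly left to a later randomised trial. The wording of the endpoint can be read as naming the sources of cost data, without ruling out a model. A detailed analysis plan is promised before database lock, and a modelling method is ordinary content for such a plan or for a health-economic plan.

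Much of this stands. The absence of a described model is not in itself a fault of the protocol. A reader might infer that the economic question cannot be answered at all, or that the data sources capture standard-care costs alone. The document supports neither reading: expenditure is directly measurable, test costs are to be retrieved, and accuracy and cost data from this cohort can feed a model. A reader might also infer that the effect of the tests is zero by design. It is not estimable here, which is different.

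What does not stand is that later planning removes the difficulty. An analysis plan can add a model, but it cannot supply a group that was never observed or turn a projection into a measurement. The hypothesis bullet, the design statement and the endpoint do not carry the introduction's qualification.

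Nor is withholding results a mistake: it keeps the tests from influencing care while their accuracy is assessed.

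**Conclusion.** The point holds in a limited form. The study can describe healthcare expenditure under standard care and the cost of the tests. It cannot observe an improvement in resource use or measure the cost-effectiveness of test-guided care, and the design statement in section 5.a.ii and the endpoint in section 4.c.iii say otherwise.

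Its size is structural: 0 of 210 participants supply data on test-guided care, so no incremental cost or effect can be computed from observation, whatever the sample size. This rests on results being withheld as planned and on no outside comparator being used; the protocol describes none. It affects one of three secondary hypotheses and the matching endpoint. The primary AUC endpoints, the sample size and data collection are untouched.

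**What to change.** Reword the secondary objective in the synopsis, the hypothesis and aim in sections 4.a and 4.b, the endpoint in section 4.c.iii and the design statement in section 5.a.ii, so that the economic aim has two parts:

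- **Observed:** healthcare costs under standard care, including cost per tBPAR episode and per infection episode, and the cost of the tests.
- **Projected:** potential cost-effectiveness from a decision-analytic model that combines the study's accuracy estimates, observed costs and test costs with explicitly stated assumptions about management change, reported with uncertainty intervals.

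State that actual improvement in resource use is a question for the randomised trial foreseen in the introduction. The model's details can go in the analysis plan.

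The cost is a wording amendment, some modelling work and a more modest economic claim. No new data, participants or change in care are needed, and results stay withheld as planned.
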